4.4.2 Exclusion Criteria

1. Dementia due to any condition other than AD, including vascular dementia (Rosen-Modified Hachinski Ischemic score ≥ 5)
2. Evidence of significant central nervous system (CNS) vascular disease on previous neuroimaging including but not limited to: cortical stroke, multiple infarcts, localized single infarcts in the thalamus, angular gyrus, multiple lacunar infarcts or extensive white matter injury
3. Clinically significant neurologic disease or condition other than AD, such as cerebral tumor, chronic subdural fluid collections, Huntington's Disease, Parkinson's Disease, normal pressure hydrocephalus, or any other diagnosis that could interfere with assessment of safety and efficacy
4. Evidence of clinically significant unstable cardiovascular, pulmonary, renal, hepatic, gastrointestinal, neurologic, or metabolic disease within the 6 months prior to enrollment. If there is a history of cancer the subject should be clear of cancer for at least 2 years prior to screening. More recent history of basal cell or squamous cell carcinoma and melanoma in situ (Stage 0) may be acceptable after review by the Medical Monitor.
5. Creatinine clearance (CL) of $<45\text{ml/min}$
6. Poorly controlled diabetes, at the discretion of the Principal Investigator
7. Concomitant treatment with NMDA receptor antagonists such as but not limited to memantine or drug combinations containing memantine, dextromethorphan (a cough suppressant), ketamine, phencyclidine (PCP), methoxetamine (MXE), nitrous oxide (N_2O) and the following synthetic opioids: pentidine, levorphanol, methadone, dextropropoxyphene, tramadol, and ketobemidone.
8. Use of vitamin E > 400 International Units (IU) per day within 14 days prior to screening
9. Use of valproic acid within 14 days prior to screening
10. Use of an active Alzheimer's vaccine within 2 years prior to screening
11. Use of a monoclonal antibody for treatment of AD within 1 year prior to screening
12. Any medical or psychiatric condition that is likely to require initiation of additional medication or surgical intervention during the course of the study

13. Any screening laboratory values outside the reference ranges that are deemed clinically significant by the PI
14. Use of an investigational drug within 30 days prior to screening
15. Suicidality defined as active suicidal thoughts during the 6 months prior to screening or at Baseline [Type 4 or 5 on C-SSRS], or history of suicide attempt in previous 2 years, or at serious suicide risk in PI's judgment
16. Major psychiatric illness such as current major depression according to Diagnostic and Statistical Manual of Mental Disorders, 5th Edition¹⁷, current or past diagnosis of bipolar disorder, schizophrenia, or any other psychiatric disorder that might interfere with the assessments of safety or efficacy at the discretion of the PI
17. Diagnosis of alcohol or drug abuse within the last 2 years
18. Abnormal laboratory tests that suggest an alternate etiology for dementia. If the patient has prior history of serum B12 abnormality, anemia with hemoglobin ≤ 10 g /dl, thyroid function abnormality, electrolyte abnormality, or positive syphilis serology the patient should be reevaluated to determine if these potential causes of dementia have been addressed. Only if these causes have been ruled out as the cause of the dementia can the patient be enrolled.
19. History of prolonged QT or prolonged QT on screening ECG (QTcB or QTcF >499 per central reader)
20. Acute or poorly controlled medical illness: blood pressure > 180 mmHg systolic or 100 mmHg diastolic; myocardial infarction within 6 months; uncompensated congestive heart failure [New York Heart Association (NYHA) Class III or IV]¹⁸
21. Known to be seropositive for human immunodeficiency virus (HIV)
22. Known to be seropositive for Hepatitis B or C, unless successful curative treatment for Hepatitis C (e.g., Harvoni) has been received and there is documentation that there is no Hep B/C virus detected 3 months after completion of treatment
23. AST or ALT >3 x upper limit of normal (ULN) and total bilirubin >2 x ULN or International Normalized Ratio (INR) >1.5
24. Prior exposure to bryostatin, or known sensitivity to bryostatin or any ingredient in the study drug
25. Any other concurrent medical condition, which in the opinion of the PI makes the subject unsuitable for the clinical study

5 PRODUCTS USED IN THIS STUDY

Active study drug, bryostatin, and a matching placebo will be provided as described below.

5.0 Bryostatin

The investigational drug product, bryostatin, is a sterile, pyrogen-free, lyophilized powder intended for IV infusion upon reconstitution and dilution. Bryostatin will be supplied in a 10 mL vial containing 0.05mg bryostatin, 2.5mg povidone lyophilized from 40% t-butanol. Accompanying

each vial of Bryostatin will be a 10mL vial containing 2mL of sterile PET diluent [60% v/v polyethylene glycol 400, 30% v/v dehydrated ethyl alcohol, and 10% v/v Tween-80 (polysorbate 80)].

5.1 Placebo

The placebo is a sterile, pyrogen-free lyophilized powder intended for IV infusion upon reconstitution and dilution. It will be supplied in a 10 mL vial containing 0.0mg bryostatin, 2.5mg povidone lyophilized from 40% t-butanol. Accompanying each vial of placebo will be a 10 mL vial containing 2mL of the same sterile PET diluent as described above for bryostatin. The placebo is identical to bryostatin in appearance, including color, consistency, volume, and odor.

5.2 Packaging and Labeling of Study Drug Kits

Study drug kits will contain 7 vials of Bryostatin for Infusion or 7 vials of Placebo for Infusion and 7 vials of PET diluent. Each kit will be identified by kit number only and assigned to a subject via the Interactive Response Technology (IRT), according to the established randomization scheme.

Study drug kits will be labeled in English according to the US FDA's current Good Manufacturing Practice (GMP) and local regulations.

The kit label will contain the following information:

Bryostatin or Placebo for Infusion Kit

Kit # XXXXX

Store refrigerated at 2-8°C.

Caution New Drug - Limited by Federal Law (US) to Investigational use.

Each kit contains 7 vials Bryostatin for Infusion, 0.05 mg bryostatin/vial or 7 vials Placebo for Infusion, 0.0 mg bryostatin per vial and 7 vials PET Diluent

Manufactured for Neurotrope by Lyophilization Technology, Inc.

Study drug vials will be labeled in English according to US FDA's current Good Manufacturing Practice (GMP) and local regulations.

Bryostatin for Infusion or Placebo for Infusion vial label will contain the following information:

Bryostatin for Infusion, 0.05mg bryostatin or Placebo for Infusion 0.0mg bryostatin

Kit # XXXXX

Store refrigerated at 2-8°C

Caution New Drug - - Limited by Federal Law (US) to Investigational use.

Each vial contains 0.05 mg bryostatin or 0.0 mg bryostatin and 2.5 mg povidone C-17.
Contains no antibacterial preservatives

Reconstitute with 1 mL PET Diluent. Swirl to dissolve

Further dilute with 9 mL sodium chloride for injection

Manufactured for Neurotrope by Lyophilization Technology, Inc.

PET Diluent vial label will contain the following information:

PET Diluent for Reconstitution of Bryostatin for Infusion or Placebo for Infusion

Lot #: XXXX

Volume: 2 mL

Caution New Drug - - Limited by Federal Law (US) to Investigational use

Each mL contains Polyethylene Glycol 400 (60%), dehydrated Ethyl Alcohol (30%) and Polysorbate 80 (10%).

For Single Use Only

Manufactured for Neurotrope by Lyophilization Technology, Inc.

5.3 Storage and Preparation of Study Drug

The study drug kits will be stored under refrigeration conditions (2-8°C) in a refrigerator, refrigerated cabinet or other refrigerated enclosure, which is securely locked and temperature continuously monitored. Access to the stored study drug kits will be restricted to the investigational site pharmacy or designated staff member.

Study drug will be prepared and dispensed for administration by a qualified member of the study staff (e.g., pharmacist, pharmacist-designee, nurse or physician trained in aseptic handling techniques). This individual will be responsible for reconstitution, dilution and preparation of study drug (active and placebo) according to the randomization assignment for each subject. The investigational drug is to be administered only according to the conditions of this protocol.

Study drug will be administered by the study PI or his/her designees. Study drug should be allowed to come to room temperature prior to administration. The study drug contains no antibacterial preservatives and must be used within eight hours of reconstitution. Study drug should be reconstituted with 1mL of PET diluent. After swirling the 10 mL vial to completely dissolve the contents, the resulting solution must be diluted immediately with 9mL of 0.9% sodium chloride (NS) injection, USP. The necessary volume of this solution to achieve the assigned dose (a 4.8 mL loading dose for the first two doses and a 4.0 mL maintenance dose for the remaining 5 doses) should then be added to an IV infusion bag containing 50 mL of normal saline. Once the infusion

bag is filled with the assigned dose, the 45±5 minute continuous infusion must be completed within 3 hours of the IV infusion bag fill.

The infusion system (IV infusion bag and tubing) should be made of a polyolefin plastic, such as polypropylene or polyethylene, or a combination of both. The use of polyvinylchloride (PVC) plastic bags and tubing is NOT to be used as plasticizer from the PVC is leached and there is absorption of bryostatin to PVC plastics.

The prepared infusion bag containing study drug should be labeled with the following information:

Protocol number

Kit/Subject number

Date and time prepared

Instructions for dosing (*e.g.*, entire contents of IV infusion bag infused within 45 ±5 minutes)

5.4 Study Drug Accountability and Disposal

Neither the Investigational Pharmacy, designated drug preparer, the PI nor any of his/her designees may provide drug to any person not enrolled in this study. Adequate records of study drug receipt and use must be maintained in order to comply with governmental regulations and with the protocol in addition to preventing unauthorized distribution.

Study drug orders, records of receipts, dispensing records, and inventory forms will be examined and reconciled throughout the study. All study drug that is used during the course of the study must be accounted for on a drug accountability form.

Unless otherwise directed, at the end of the study all unused study medication must be destroyed onsite following the site's specific SOPs after drug accountability has been verified by the monitor. If destruction on site is not possible, study medication should be retained and returned to Singota Solutions at the end of the study. A copy of all completed drug accountability forms will be collected by the monitor or appropriate designee upon completion of the study.

Note: The medications should not be disposed of prior to monitoring and approval.

5.5 Randomization

Once all eligibility criteria for the study have been met, and the site has received approval by the Medical Monitor (MM) and Clinical Assessment Technologies (CAT) group, via the EDC system, the subject can be randomized via Interactive Response Technology (IRT) system. A randomization number will be assigned, and drug for that randomization number will be shipped to the site for twelve weeks of treatment. Randomization and scheduling of the first study drug infusion should be timed to allow for receipt of study drug prior to the scheduled study treatment. The drug kits will be shipped to the individual who will be responsible for kit storage and drug preparation and may not be handled by any other study staff member. The study drug kit will not identify the vial containing study drug as either placebo or bryostatin.

5.6 Blinding

All subjects, PIs, and investigational clinical site personnel will be blinded to dose assignment.

Since there is no known antidote to bryostatin, the blind should only be broken in exceptional circumstances and is at the discretion of the PI. The Medical Monitor should be contacted as soon as possible to discuss the situation, but this should not delay any treatment.

In a non-emergency situation, when unblinding is requested, the site should discuss the clinical circumstances with the Medical Monitor to determine if breaking the blind will alter the subject's treatment. The decision to break the blind is ultimately the decision of the PI. If the blind is broken for a subject, the PI will record the date and reason for breaking the blind in the electronic case report form (eCRF) and study drug treatment will be discontinued. However, the subject will continue to be monitored per protocol for safety and efficacy.

5.7 Study Drug Administration

Study drug is scheduled to be administered by continuous intravenous infusion only, via a pump, at the same rate over 45 minutes (± 5 min) once a week for 2 weeks and then every 14 days ± 2 days thereafter. The entire volume of study drug in the infusion bag is to be administered. Infusion times should not be extended or shortened. If a subject misses a dose, the dose should be administered as soon as possible. The subject should then continue on the original dosing schedule. Provided all efficacy assessments have been completed, if deemed necessary by the PI, a short acting sedative may be administered to reduce a subject's anxiety or agitation during the infusion. All medication is to be recorded on the Concomitant Medication eCRF.

6 STUDY PROCEDURES AND ASSESSMENTS

Subjects will be randomized to study drug, either bryostatin or placebo treatment. A follow-up visit will take place 30 days after the last dose of study drug for all subjects, including subjects that have discontinued treatment before completion of the study. Assessments will be performed according to the Schedule of Activities (Table 1).

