7.7 Criteria for Withdrawal of Subjects

Subjects may be withdrawn from the clinical study for the following reasons:

- The PI believes withdrawal to be medically necessary or in the best interest of the subject
- Noncompliance with the protocol as judged by the PI (requires discussion with the Sponsor)
- Subjects who are enrolled in violation of inclusion and/or exclusion criteria
- An AE that presents an unacceptable consequence or risk to the subject as judged by the PI, Sponsor or the Medical Monitor
- Lost to follow up
- Withdrawal of consent
- Subject is unblinded

Subjects may voluntarily discontinue their participation in the study at any time without prejudice to further treatment.

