9.0 Sample Size Determination

Based on post hoc analyses of the NTRP 101-202 study for patients not treated with memantine, the SIB for the 20ug bryostatatin group demonstrated a mean (SD) increase of 4.5 (6.8) points from baseline by Week 13. In contrast, patients not treated with memantine in the placebo arm showed a decrease in SIB scores at the 13-week time-point from baseline, giving a mean (SD) SIB change of -0.9 (6.7) points. This resulted in group difference in means of the 13-week SIB measure from baseline SIB changes of 5.4 points.

Guided by these post hoc results, power analyses were performed based on 50 patients per treatment arm, and assuming differences of between 4.0 to 5.5 points in the treatment arm-specific means of the primary outcome (e.g. the treatment effect). Table 2 below gives the estimated power to detect various treatment effects, assuming a two-sided alpha of 0.05. Based on these analyses, 50 patients per group will give an approximate 83% power to detect a treatment effect of 4.0 points, and an estimated power of 98% to see a treatment effect of 5.5 points. Power calculation was based the two-sample t-test of the group difference in the mean 13-week SIB changes from baseline SIB.

Table 2: Power to detect treatment effect sizes of between 4.0 to 5.5 points; 50 patients per group with an available primary efficacy endpoint.

Diff. in Deltas	Power	N1	N2	Two-sided Alpha
4.0	83%	50	50	0.05
4.5	91%	50	50	0.05
5.0	95%	50	50	0.05
5.5	98%	50	50	0.05

Power analyses were also preformed to determine detectable effect sizes that assume an estimated dropout rate of 25% (e.g. 50 patients per group at a baseline, dropping to 37 patients per group by Week 13). Table 3 gives the estimated powers for treatment effects of between 4.5 and 5.5 points, assuming a 25% dropout rate. Note that a minimum treatment effect of 4.5 points can be statistically detected with at least 80% power, given 37 patients per group with a primary efficacy endpoint.

Table 3: Power to detect treatment effect sizes of between 4.5 to 5.5 points; 37 patients per group with an available primary efficacy endpoint.

Diff. in Deltas	Power	N1	N2	Two-sided Alpha
4.5	80%	37	37	0.05
5.0	88%	37	37	0.05
5.5	93%	37	37	0.05

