9.4 Analysis of Primary Efficacy Endpoint

The primary endpoint for this study is the change from baseline to Week 13 in the SIB total score. The primary analysis will be conducted on FAS population. The CAS population will be used as a supportive analysis. All statistical tests for efficacy will be two-sided tests, with $\alpha=0.05$.

Based on the review of patients not treated with memantine in the NTRP 101-202 clinical trial, the expected number of patients who will drop out of the study prematurely will not be significant. For efficacy evaluations, multiple imputation methods will be used to handle missing data. This imputation method is a robust method to impute missing measurements. The imputation will be carried out in SAS version 9.4 or later using PROC MI. Each imputation model will include the stratification factor (i.e., MMSE-2 score (4-9 vs. 10-15)) as a covariate in the model..

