7.3 Handling of Missing Data

Every effort will be made to obtain required data at each scheduled evaluation from all subjects who have been randomized to minimize missing data. However, in the event when there is missing data the following imputation methods will be used.

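### No procedure tells subjects who stop study drug to attend Week 13, so primary SIB values that could be observed for up to about half of early withdrawals would be imputed

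*Protocol*

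**What the plan says.** Protocol section 6 schedules a follow-up visit 30 days after the last dose for all subjects, "including subjects that have discontinued treatment before completion of the study". Section 6.2.11 gives the same visit to subjects who have withdrawn from the study, and Table 1 puts Week 15 and early termination in one column. The visit includes the SIB. Section 7.8, on stopping study drug, does not say whether later visits continue.

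On unblinding, section 5.6 says that drug is stopped but "the subject will continue to be monitored per protocol for safety and efficacy". Section 7.7 lists "Subject is unblinded" among the reasons for which a subject may be withdrawn from the study.

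SAP 7.3 states: "Every effort will be made to obtain required data at each scheduled evaluation from all subjects who have been randomized". Protocol 6.1 makes a similar general commitment to complete required tests. Efficacy values that are still missing are multiply imputed (Protocol 9.4, SAP 7.3.1). Protocol 9.0 includes power analyses that "assume an estimated dropout rate of 25" percent, taking 50 per group to 37 with a Week 13 value, whereas Protocol 9.4 expects early dropout not to be significant.

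**The concern.** The primary endpoint is the SIB change at a single visit, Week 13. The protocol ties its one specified visit for subjects who stop drug to the last dose, and it uses that same visit for subjects who leave the study. A site reading this cannot tell whether to book the Week 13 SIB for someone who has stopped infusions but remains willing to attend.

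If sites do not book it, a value that could have been measured becomes a missing value, and the full analysis set result leans on multiple imputation. The SAP body gives no sensitivity analysis for the imputation assumption. The completer set cannot serve as one, because it requires completed treatment and so leaves these subjects out. Adverse events were the second most common reason for early withdrawal in the previous study, so discontinuation related to tolerability, and hence possibly to arm, is a real prospect.

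**Working it through.** **Does the 30-day visit stand in for Week 13?** Table 1 places doses 1 to 7 on days 0, 7, 21, 35, 49, 63 and 77. Week 13 is day 91 ±2, that is days 89 to 93.

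| Last dose | Nominal day | Plus 30 days | In days 89–93? |
|---|---|---|---|
| 1 | 0 | 30 | No |
| 2 | 7 | 37 | No |
| 3 | 21 | 51 | No |
| 4 | 35 | 65 | No |
| 5 | 49 | 79 | No |
| 6 | 63 | 93 | Yes, on the edge |

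Subjects who receive dose 7 have completed dosing and are not at issue. Even after dose 6, the SAP text provided has no visit-window rule that would map the SIB to Week 13.

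**How much could be recovered?** Protocol 2.1.3 reports 35 early withdrawals among 141 treated subjects in the previous study (35/141 = 24.8%), of which 18 were withdrawal of consent and 11 were adverse events.
- Not withdrawing consent: 35 − 18 = 17, and 17/35 = 49%.
- If the 18 are counted against the 29 withdrawals in the full analysis set instead: (29 − 18)/29 = 38%.
- Planned losses here are 50 − 37 = 13 per arm. 13 × 17/35 = 6.3 per arm, about 12 to 13 in total, so missingness would fall from 13/50 = 26% to about 13%.

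**How much of the full analysis set would be imputed?** That set excludes subjects with no post-baseline efficacy assessment. In the previous study it had 135 subjects, and 113 subjects had a Week 13 SIB. If all 113 belong to the set, 135 − 113 = 22 were missing, and 22/135 = 16%.

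**Power: the plan's own figures first.** Inputs are from Protocol 9.0: active arm "mean (SD) increase of 4.5 (6.8) points from baseline by Week 13", placebo "mean (SD) SIB change of -0.9 (6.7) points". Pooled SD = √((6.8² + 6.7²)/2) = 6.75. "All statistical tests for efficacy will be two-sided tests, with" alpha 0.05 (Protocol 9.4). The method is the two-sample t-test, with noncentrality = difference / (SD × √(2/n)).

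| n per arm | Difference | Stated | Recomputed |
|---|---|---|---|
| 50 | 4.0 | 83% | 83.5% |
| 50 | 4.5 | 91% | 91.0% |
| 50 | 5.0 | 95% | 95.6% |
| 50 | 5.5 | 98% | 98.1% |
| 37 | 4.5 | 80% | 80.8% |
| 37 | 5.0 | 88% | 88.2% |
| 37 | 5.5 | 93% | 93.3% |

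The plan's powers reproduce. The 37-per-arm table has no 4.0-point row; power there is 71.0%.

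**Power if about half are recovered.** Take 44 per arm: 37 on drug plus 7 off drug, which is 13/2 rounded up. The documents give no off-drug effect, so the share kept is an assumption. The average difference is 4.0 × (37 + 7 × share)/44; any added variance from mixing on-drug and off-drug subjects is ignored.

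| Share of effect kept off drug | Average difference | Power |
|---|---|---|
| All | 4.00 | 78.5% |
| Half | 4.0 × 40.5/44 = 3.68 | about 72% |
| None | 4.0 × 37/44 = 3.36 | about 64% |

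The comparison is 71% with 37 per arm and no recovery.

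**Bias from imputing.** Suppose 25% of active-arm values are imputed as if still on treatment and the target is the effect regardless of stopping. The overstatement is 0.25 × (effect lost off drug): 0.25 × 4 = 1.0 point if all 4 points are lost, 0.25 × 2 = 0.5 if half, and 0 if none.

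**The case against.** The strongest reply is that the protocol nowhere removes off-drug subjects from the schedule. Section 6 adds a 30-day visit for everyone, completers included, and its next sentence applies Table 1 without exempting those off drug. Sections 7.7 and 7.8 separate leaving the study from stopping drug. Section 5.6 and SAP 7.3 both lean towards continued assessment. The completer set asks for completed treatment and a Week 13 SIB as two conditions, which allows for one without the other.

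This stands as far as it goes. A reader might infer that subjects who stop drug are barred from Week 13; the documents do not say so. What remains is that the effort statements are general, 5.6 covers only unblinded subjects, and no procedure directs other off-drug subjects to Week 13.

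A second reply is that the 5.6 and 7.7 conflict is mild: 7.7 is permissive, and unblinding is reserved for exceptional circumstances. Both points are fair. The two sections still leave the follow-up of an unblinded subject undecided.

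Third, the 1.0-point figure presumes an imputation model and an estimand that the plan does not state. SAP 7.3.1 requires only the MMSE-2 stratum as an imputation covariate and does not mention treatment. If treatment were left out, imputed values would be pulled towards no difference. This objection stands in full.

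**Conclusion.** The concern holds as a gap in the follow-up rule together with an inconsistency between sections. The only specified visit after stopping drug misses Week 13 unless dose 6 was the last, and no procedure fills the gap. Week 13 values that could be observed for up to about half of early withdrawals would be imputed.

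Three stronger readings are not supported:
- **Most of the 25% could be observed.** About half of earlier withdrawals were withdrawal of consent, and the 25% is a dropout figure that does not separate stopping drug from leaving the study. The share of the full analysis set imputed may be nearer 16%.
- **Follow-up would restore power.** The range of 64% to 78.5% straddles the 71% without recovery. The stated sample size and powers are not in error.
- **The result would be overstated by a point.** An overstatement of 0 to about 1 point applies only if 25% are imputed as on treatment. The size, and even the direction, depend on the off-drug effect, the imputation model and the estimand, none of which is given.

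The 17-of-35 split comes from a three-arm study that included a 40 µg arm and memantine users, so it may differ here. Some of those 17 may also have been unreachable. The benefit that does not depend on these unknowns is that observed values replace imputed ones, and an off-drug SIB, once collected, can be used or set aside according to the estimand.

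**What to change.** In Protocol sections 6 and 6.2.11, state that a subject who stops study drug without withdrawing consent remains on the SIB schedule, at minimum Week 13, in addition to the 30-day visit. Record a flag on SIBs obtained off drug and on SIBs rated after unblinding. Reconcile sections 5.6 and 7.7 so that sites know whether an unblinded subject stays in follow-up. In the SAP, say how flagged values enter the primary analysis.

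The cost is a protocol amendment and attendance at visits already in Table 1 for roughly a dozen subjects (26 planned losses × 17/35 ≈ 13). The downside is some caregiver burden, and attendance will be partial.
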